**MATERIAL REQUIREMENT:**

1. Drugs as prescribed
2. Dressing pack
3. Sterile gloves
4. Povidone iodine 10% or Chlorhexidine in 70% alcohol or alcohol swab
5. 2 x 50ml leuc lock syringes (for Alteplase & Pulmozyme)
6. 2 x 10ml syringes (to flush)
7. 2 x Blunt ended drawing up needles
8. 0.9% NaCL total 750ml
9. 3-way tap connector
10. Rubbish bag
11. Dressing trolley

**1. PREPARATION CHART t-PA (ALTEPLASE)/ACTILYSE®:**

**A) Reconstitution**

- 1) Wipe the top of the vial with 60-70% alcohol swab.
- 2) Insert cannula into **Sterile Water Vial** (provided in the box).
- 3) Empty water into **Actilyse® 50mg Vial**.

- 4) Mix by gentle swirling/ slow inversion. **DO NOT** shake. Allow to stand if foam is present. Final concentration = **1mg/mL (50mL)**.

**B) Administration**

**STEP 1**

Syringe out **dose** required (eg: if 16 mg = 16 ml)

**Reconstituted Alteplase solution**  
1mg/mL (50mL)

**50mL Syringe**

Further dilute with normal saline up to **final volume of 50ml**

**STEP 2**

Wrap balance Alteplase solution with parafilm, label date and time open and keep in fridge. (stable for 24 hours)

[figure not shown]
## 2. PREPARATION CHART – DNase (PULMOZYME) :

- DNase (Pulmozyme) must be stored **in the refrigerator at 2-8°C** and protected from light & heat.
- Do not use the medicine if it has been exposed to room temperature for more than 24 hours.
- The solution should be discarded if it is cloudy or discoloured.
- DNase (Pulmozyme) contains no preservative and, once opened, the entire ampoule must be used or discarded.

[figure not shown]
- a) Open the foil pouch and remove only **2 ampoules (2x2.5mg=5mg)** of DNase (Pulmozyme) from its pouch each time before instillation. Keep the other ampoules back into fridge.

- b) Hold the tab at the base of the ampoule of DNase (Pulmozyme) firmly, taking care not to squeeze the body of the ampoule, and twist off the

- c) Syringe out the full dose of the drug from 2 ampoules of DNase (Pulmozyme) (2 x 2.5ml) until the ampoule is empty.

- d) Wrap the 50ml syringe with diluted DNase (Pulmozyme) with parafilm, label date and time of preparation. Do not use the medicine if it has been exposed to room temperature for more than 24 hours.

## **PROCEDURE OF INSTILLATION OF t-PA/DNase**

1. Premedication (Tramadol) for pain relieve before each dose. Medication to be given at least 20 minutes before the procedure.
2. Draw up Alteplase & DNase as prescribed (Refer Section 6 & 7 of protocol).  
Prepare 2 x 10ml 0.9% NaCL in syringes for flushing purpose.
3. Check all connections are secure.
4. Uncap the outer port.
5. Clean the port thoroughly with Chlorhexidine, Povidone iodine 10% or alcohol swab.
6. Turn the 3-way tap to off the position to the chest.
7. Attach the 10cc syringe filled with NS to the outer port and turn the 3 way tap towards the chest.
8. Flush the drain with 5 ml NaCL (pre-Alteplase) to check patency.
9. Turn the 3 way tap to off the position to the chest.
10. Attach 50cc syringe containing diluted Alteplase, turn back the 3 way tap towards the chest and inject slowly within 1-2 minutes.
11. Disconnect and flush with 5ml NaCL towards the chest (post-Alteplase).
12. After flushing, keep the 3-way tap turned off to the chest and clamp for 45 minutes.
13. Attach new bung to the outer port.
14. After clamping, open the 3-way tap to drain towards the bottle for 45 minutes, record drainage prior to second instillation.
15. After 45 minutes of drainage, repeat process with DNase (Pulmozyme). Flush the drain with 5 ml NS (pre-Pulmozyme).
16. Turn the 3 way tap to off the position to the chest.
17. Attach 50cc syringe containing diluted DNase (Pulmozyme), turn back the 3-way tap towards the chest and inject slowly within 1-2 minutes. Followed by a 5ml NS flush (post-Pulmozyme).
18. After flushing, keep the 3-way tap turned off to the chest.
19. After 45 minutes of clamping, open the 3-way tap to drain towards the bottle and record the drainage until next instillation.

## **OBSERVATION AFTER ADMINISTRATION OF t-PA (ALTEPLASE) & DNase (PULMOZYME)**

1. Observe the patient for:
  - a. deterioration in clinical condition
  - b. tension pneumothorax
  - c. hemorrhage from site or excessive drainage (in excess of 1L per hour) in drainage bottle
2. Monitor for:
  - a. Bedside ultrasound of thorax (by chest physician) daily with curvelinear probe (ultrasound Mindray, model Z5) by measuring the maximum distances between the parietal and visceral pleural.
  - b. Serial chest x-ray (baseline x-ray, day 7 post t-PA/DNase and pleural irrigation)
  - c. Serum CRP level (baseline, day 7 post t-PA/DNase and pleural irrigation)
  - d. FBC (baseline, day 1- 3, day 7 post t-PA/DNase and pleural irrigation). Drop of

hemoglobin by less than 10% from baseline is acceptable.

- e. Systemic bleeding/ Pleural bleeding
  - f. Drainage of pleural effusion daily
3. Stop the t-PA & DNase if there is significant drop of haemoglobin (>10% drop Hb) with clinical signs of shock or significant haemorrhagic fluids drained. Consider CTA and blood transfusion in those cases

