### 2.3 Secondary Objectives:

- To determine the reduction of pleural opacity (in percentage) on chest radiograph from day 1 (randomization) to day 7
- To determine the change on inflammatory markers (WBC/CRP) from day 1 (randomization) to day 7
- To determine the outcome :
  - Length of hospital stay (in days) after randomization for each group
  - The need of surgical intervention in 30 days
  - Adverse effects following t-PA/DNase and pleural irrigation
  - Mortality rate at 30 days

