### Medication Regimen :

t-PA (Alteplase) 5mg and DNase (Pulmozyme)5mg

t-PA (Alteplase) that is available in our pharmacy is 50mg ampoule and DNase (Pulmozyme) is 2.5mg per ampoule

The number of installation of intrapleural t-PA/DNase depends on the discretion of the treating physician (at least 6 hours apart between each dose). 5mg of Alteplase (t-PA) and 5mg DNase are diluted in each 50ml of 0.9% sodium chloride solution. t-PA and DNase are not mixed together in one syringe. The detailed method of t-PA/DNase therapy administration is described in Appendix 1. In brief, both medication are administered sequentially which t-PA is first instilled intrapleurally and the chest tube is then clamped for 45 minutes, then unclamped to allow free drainage for 45 minutes. The same procedure is then repeated for DNase. Selection of the timing of treatment and removal of chest tube are depending on the chest physician's judgement.

However, as for patients who were randomized into pleural irrigation group, subjects were administered 250 ml of 0.9% sodium chloride via chest tube a three way tap from a drip stand which were allowed drainage freely over 1 hour. Pleural irrigation will be performed minimum of 3 installations and maximum of 9 installation (3 times per day).

Both groups received standard care of treatment : which includes regular flushing of chest drain to maintain patency using 20mls of normal saline.

The primary outcome was to evaluate the volume of pleural effusion drainage (in mls) 72 hours following randomization. The volume drained measured after subtracting the amount of volume administered as per protocol.

The secondary outcome are measured by the change in the area of pleural opacity in chest x-ray (day 7 post t-PA/DNase compared to baseline), measured as the percentage of the ipsilateral hemithorax occupied by effusion. The area of pleural opacity and the area of the ipsilateral hemithorax will be measured digitally by two radiologists using Horos Project Software, v3.2.1 as described previously in Multicentre Intrapleural Sepsis Trial 2 (MIST-2)

Other outcomes that will be monitored include :

1. Inflammatory markers including serum C-reactive protein (CRP) & white blood count
2. Length of hospital stay in days
3. The need of surgical intervention within 30 days
4. Adverse effects :
  - a. Chest pain required escalation of analgesics
  - b. Systemic bleeding
  - c. Pleural bleeding

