During any point of treatment subjects will be allowed to cross-over and analysis will be done as per intention to treat. Subjects in the pleural irrigation group may be switched to IPFT group if there is poor response to treatment (poor drainage of effusion), or adverse effects of irrigation as per clinician's judgement. On the contrary, subjects in the IPFT group may be switched to pleural irrigation group if patient developed any adverse effects of IPFT (e.g hemothorax, haemoptysis). Those who failed both treatment will be referred for surgical intervention

Monitoring Parameters :

a. Pleural irrigation group

Parameter	Day0	Day1	Day2	Day3	Day7	Day30
Investigations						

 
• Full blood count (FBC)               
 
○ WBC
 
○ Hemoglobin
 
 
 
	√	√	√	√	√	
• C- reactive protein (CRP)	√				√	
• Chest X-ray	√				√	
• Ultrasound Thorax	√	√	√	√		
Adverse effects						
• Chest pain required escalation of analgesics		√	√	√		
• Gastrointestinal bleed		√	√	√		
• Bleeding from chest drain site		√	√	√		
• Intrapleural hemorrhage		√	√	√		
• Hemoptysis		√	√	√		
• Clinical deterioration – hypotension, dyspnea		√	√	√		
• Hb drop >10% required transfusion blood		√	√	√		
• Death related to intrapleural saline irrigation		√	√	√		

Others Outcome						
• Mortality						
• Surgical intervention						

b. IPFT group

Net Volume of pleural fluid drained (ml) post pleural irrigation	Baseline	Day 1	Day 2	Day 3
	√	√	√	√
Cumulative pleural fluid drained post pleural irrigation				√

b. Intrapleural fibrinolytic group

Parameter	Day0	Day1	Day2	Day3	Day7	Day30
Investigations						
• Full blood count (FBC) 
 
○ WBC
 
○ Hemoglobin
 
	√	√	√	√	√	
• C- reactive protein (CRP)	√				√	

• Chest X-ray	√				√	
• Ultrasound Thorax	√	√	√	√		
Adverse effects						
• Chest pain required escalation of analgesics		√	√	√		
• Gastrointestinal bleed		√	√	√		
• Bleeding from chest drain site		√	√	√		
• Intrapleural hemorrhage		√	√	√		
• Hemoptysis		√	√	√		
• Clinical deterioration – hypotension, dyspnea		√	√	√		
• Hb drop >10% required transfusion blood		√	√	√		
• Death related to intrapleural therapy		√	√	√		
Others Outcome						
• Mortality						
• Surgical intervention						

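### Tension pneumothorax and drainage above 1 L per hour are on the bedside observation list, but the adverse-effect forms have no field for either

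*Combined protocol and SAP*

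**What the plan says.** Section 2.3 lists "Adverse effects following t-PA/DNase and pleural irrigation" among the secondary objectives, so harms are to be compared between the arms.

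The observation part of Appendix 1 stands under a heading that names t-PA and DNase only. Its item 1 tells staff to watch for clinical deterioration, for "tension pneumothorax", and for "hemorrhage from site or excessive drainage (in excess of 1L per hour) in drainage bottle". Item 2 lists monitoring tests, and three of these (2b to 2d: chest x-ray, CRP, blood count) name both treatments, for example "Serial chest x-ray (baseline x-ray, day 7 post t-PA/DNase and pleural irrigation".

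The recording side is in three places:

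- The outcome list in section 3.6 names three adverse effects: "Chest pain required escalation of analgesics", systemic bleeding and pleural bleeding.
- The Monitoring Parameters tables in section 3.6, one per arm, have eight adverse-effect rows each, ticked on Days 1 to 3. They include "Bleeding from chest drain site" and "Clinical deterioration – hypotension, dyspnea". Drained volume is entered per day from baseline to Day 3, with one cumulative total.
- The Outcome Monitoring page of the Data Collection Sheet repeats the eight rows and the daily volumes.

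Section 3.6 also says, in its closing paragraph on data collection, that adverse events and the occurrence of complications are recorded. It names no event there.

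**The concern.** An observation list and a recording form should match. Here the list directs attention to two events for which the form has no field, and a closed form without a line for other events gives staff nowhere to enter them. If either event occurs, it may be seen and managed at the bedside and still not be identifiable in the data.

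Drained volume is the primary outcome. Drainage that the protocol itself calls excessive would therefore enter the dataset only as a larger volume, with nothing to mark it as an alert.

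The lack of an open line matters for irrigation too. Section 3.6 allows a switch to fibrinolytic therapy for adverse effects of irrigation on the clinician's judgement, but an effect outside the eight rows has no place on the form.

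Finally, item 1 of the observation list is headed for one arm of an open-label trial. A reader cannot tell whether irrigation patients are to be observed for the same things.

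**Working it through.** The plan states no figure on this point, so the main check sets the observation list beside the forms.

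**Step 1. Does each item in the list have a field?**

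| Item 1 of the observation list | Nearest field in both arms' tables and the data sheet | Identifiable from the form? |
|---|---|---|
| Clinical deterioration | Clinical deterioration row | Yes |
| Tension pneumothorax | Same row | Not by cause; looks the same as deterioration from sepsis or bleeding |
| Haemorrhage from site | Drain-site bleeding; intrapleural haemorrhage | Yes |
| Drainage above 1 L per hour | Daily net volume and cumulative total | No |

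**Step 2. Can the missing items be recovered from other planned data?**

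- Drainage rate: a daily total does not determine an hourly rate. As an illustration, 1,200 ml in a day may be 1,200/24 = 50 ml in every hour, or more than 1 L in a single hour. A small total makes such an hour unlikely; a large one does not establish it.
- Pneumothorax: the chest x-ray is scheduled on Day 0 and Day 7 and is read for area of opacity. The daily ultrasound is specified as a distance between the pleural layers. Neither is specified to record pneumothorax on Days 1 to 3.

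**Step 3. Are the arms treated alike?**

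| Element | t-PA/DNase | Irrigation |
|---|---|---|
| Eight adverse-effect rows, Days 1 to 3 | Yes | Yes |
| Blood count, CRP, x-ray and ultrasound schedule | Same | Same |
| Item 1 observation list | Yes, by heading | Not stated |

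The asymmetry is confined to the last row.

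**Step 4. Would a drainage-rate row be comparable between arms?** Only if it is net of fluid put in. Irrigation uses 250 ml, and 250/1,000 = 25% of the alert level. A t-PA or DNase instillation is 50 ml plus two 5 ml flushes, so 60 ml, and 60/1,000 = 6%. If all the fluid returned within the hour, a gross count would reach 1 L with 750 ml of the patient's own fluid after irrigation and 940 ml after an instillation. Section 3.6 already subtracts administered volume for the primary outcome.

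**Step 5. How many events might there be?** The documents give no rate, so the rates here are assumptions. With the 39 per arm of section 3.3, the chance of at least one event in an arm is 1 − (1 − p)^39:

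- p = 1%: 1 − 0.99^39 = 32%
- p = 2%: 1 − 0.98^39 = 55%
- p = 5%: 1 − 0.95^39 = 86%

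A recorded zero in 39 would give a one-sided 95% upper limit of 1 − 0.05^(1/39) = 7.4%. Without a row, the absence of an entry is not a recorded zero, and that limit cannot be claimed.

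**The case against.** The strongest reply is that the events are not lost. Section 3.6 says complications are recorded, and a symptomatic tension pneumothorax would fit the clinical deterioration row. It would then be counted, though not by cause. The haemorrhage half of the quoted item has rows of its own, and the drainage half is written as a bedside alert, not as an adverse event. In the t-PA/DNase arm, Appendix 1 also has staff record drainage after a timed 45-minute window, which gives a rate at the bedside.

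Most of this stands, and it limits the point to specificity. It does not remove it: the general statement has no matching field, the deterioration row does not show cause, and the timed reading does not reach the data sheet.

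Three stronger readings are tempting, and the documents do not support them:

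- *Foreseen harms go uncounted.* The general statement and the deterioration row prevent that conclusion. The protocol also tells staff to watch for these events; it does not say that it expects them.
- *Closer watching in one arm biases the safety comparison.* The rows, days, blood counts and ultrasound are the same in both arms. The list sits in an appendix about giving t-PA and DNase, which explains its heading. No irrigation list appears in the text available, but the section 3.7 flow chart was not available to check.
- *Very fast drainage is scored as success.* It adds to the primary volume, but treatment success in section 3.6 also requires less opacity, resolved inflammatory markers and no surgery within 30 days.

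**Conclusion.** The concern holds as a gap in the recording forms. Two events that staff are told to observe for cannot be identified or compared by arm from the planned tables or the data sheet, although adverse effects in both arms are a secondary objective. The finding rests on the printed rows of those forms and assumes that no other form captures the events.

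Its effect on the safety comparison cannot be sized. One event is 1/39 = 2.6 percentage points of an arm, but that is true of any event and shows no distortion. The probabilities in the working show only that counts could be small over the assumed rates. The difference between arms is limited to whether item 1 of the observation list covers irrigation. This is a cheap improvement, not a flaw that undermines the trial.

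**What to change.** Add three rows to both arms' tables in section 3.6 and to the Data Collection Sheet, and report them by arm with the other adverse effects:

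1. Pneumothorax, with tension or other to be marked.
2. The protocol's own excessive-drainage alert, recorded net of instilled, flush or irrigation fluid so that the arms are comparable. The bedside alert itself stays as written.
3. Other adverse event (specify).

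Separately, reconcile item 1 of the observation list in Appendix 1, which is headed for t-PA/DNase only, with items 2b to 2d and the section 3.6 tables, which cover both arms. The investigators should state whether item 1 applies to irrigation; this review does not say which answer is right.

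The cost is three form rows, one clarifying sentence and slightly more recording. The volumes put in must already be known to compute the primary outcome, but the drainage row also needs the hourly figure to be noted when the alert is met.

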### Data Collection Sheet

**Open label controlled trial of pleural irrigation with normal saline versus intrapleural fibrinolytic with tissue plasminogen activator and DNase in Pleural Infection in Universiti Kebangsaan Malaysia Medical Centre (UKMMC)**

Patient's ID sticker

Date of admission:

Admission ward:

Date of discharge :

Phone number:

#### Inclusion criteria

- Adult patient with aged  $\geq 18$  year old
- History of fever and /or elevated inflammatory markers such as elevated CRP/WBC
- Radiological evidence of complicated pleural effusion or empyema

#### Exclusion criteria

- Known allergy or sensitivity to DNase or t-PA
- Acute stroke
- Major haemorrhage or major trauma in last 6 months

Information sheet given  If yes, proceed to data collection ⇨

Demographic	
Gender	Male / Female
Age	Years
Ethnicity / Race	Malay  Chinese  India  Others 
Occupation	
Smoking history	Smoker  ..... packs/year Ex- smoker  .....packs/year Non smoker 
Allergy history (If yes, state the name of drugs/food)	

 Tick the appropriate box	Yes	No
--	-----	----

Comorbidities		
Diabetes mellitus		
Hypertension		
Dyslipidemia		
Ischemic heart disease		
Congestive cardiac failure (CCF)		
Stroke/ TIA > 3 months duration		
Atrial fibrillation (If yes, state type of anticoagulant)		
Valvular heart disease		
Bronchial asthma		
Chronic obstructive lung disease (COPD)		
Lung fibrosis		
History of pulmonary tuberculosis (If yes, state whether on treatment)		
Chronic liver disease		
End stage renal disease		
Malignancy If yes, state site of primary disease & stage, whether chemo/radiotherapy?		

Medications/ drug history:	
-----------------------------------	--

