### 3.4 Inclusion and Exclusion Criteria

#### Inclusion Criteria

1. Adult patient with aged  $\geq 18$  years old
2. Patients with pleural infection (complex parapneumonic effusion or empyema) with poor pleural fluid drainage of  $\leq 150$  ml after 24H of insertion of chest drain
3. Clinical features consistent with pleural infection ; fulfilling  $\geq 2$  of the following characteristics :
  - i) Clinical evidence of infection such as fever and or elevated C-reactive protein (CRP) or total white blood count (TWBC)
  - ii) Complex pleural effusion proven by thoracic ultrasound is defined as presence of fibrin strands or septations within pleural cavity
  - iii) Pleural fluid that fulfil at least one of the characteristic :
    - frank pus,
    - exudative type of pleural effusion (according to light's criteria)
    - gram stain or culture positive
    - lactate dehydrogenase (LDH)  $> 900$ U/L
    - Acidic with  $\text{ph} < 7.2$
    - glucose level  $< 3.3$  mmol/L

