#### Exclusion criteria

1. Refusal to participate
2. Known allergy to t-PA or DNase
3. Acute stroke
4. Significant bleeding diathesis/ active gastrointestinal bleed
5. Major surgery in the previous 5 days
6. Previous pneumonectomy on the infected side
7. Bronchopleural fistula
8. Pregnancy

9. Coagulopathy (INR > 2, APTT > 100)
10. Platelet count < 50000 cells

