### 3.6 Recruitment/Data Collection

Subjects with pleural infection (complex parapneumonic effusion or empyema) with poor outflow  $\leq 150$ cc pleural fluid from chest drain over 24 hours of insertion with standard medical therapy who are eligible for this study will be offered to participate into this study. Patient will be informed that this is an 'off label' drugs and a written informed consent will be obtained.

All patients will undergo chest tube/drain insertion. The decision to insert chest drain, the size of chest drain and when to initiate intrapleural t-PA/DNase is determined by the chest physician.

Ultrasound of thorax and chest radiograph will be performed within 24 hours before randomization. Ultrasound of thorax is performed by chest physician with curve probe (ultrasound Mindray, model Z5) for confirmation of complex pleural effusions and chest tube's position. Complex pleural effusion on ultrasound is defined as fibrin strands or septa within the pleural effusion along with presence of loculations in pleural cavity. A baseline chest radiograph will be performed within 24 hours prior to intrapleural fibrinolysis or pleural irrigation to ensure the chest tube position.

Demographic data was collected prior to randomization, which consist of age, gender, ethnicity, BMI, comorbidities. Subjects will be randomized with a block of 4 (using sealed envelope) with random permutations of 2 groups : pleural irrigation group and intrapleural t-PA and DNase.

All patients that prescribed intrapleural t-PA/DNase during the study period will receive a standard dose of medications as below (Appendix 1).

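### The eligibility checklist on the Data Collection Sheet does not match section 3.4: it omits most exclusions and all coagulation and platelet limits, and adds one exclusion of its own.

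*Combined protocol and SAP*

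**What the plan says.** Section 3.4 defines eligibility. Its inclusion criteria require an adult with pleural infection whose drain has yielded no more than 150 "ml after 24H of insertion of chest drain". They also require at least two of three features: clinical evidence of infection, a complex effusion on ultrasound, and at least one of six pleural-fluid findings. Its ten exclusions begin with "Refusal to participate" and "Known allergy to t-PA or DNase". They include "Significant bleeding diathesis/ active gastrointestinal bleed" and two laboratory items: a platelet count below 50000, and the clotting item, which reads "Coagulopathy (INR > 2, APTT > 100".

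The Data Collection Sheet prints a second pair of inclusion and exclusion lists. Its inclusion list has three items: age, "History of fever and /or elevated inflammatory markers such as elevated CRP/WBC", and radiological evidence of a complicated effusion or empyema. Its exclusion list also has three: allergy or sensitivity to either drug, acute stroke, and "Major haemorrhage or major trauma in last 6 months". A line asking whether the information sheet was given comes next, and the form then moves on to data collection.

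No text describes the sheet as an abbreviated list, and none says which list prevails where they differ.

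**The concern.** A shortened checklist would normally be a subset of the protocol's list. This one is not, because it drops criteria and also adds one. The two lists therefore conflict in both directions, and a reader cannot tell which population the trial intends to enrol.

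Two things are at stake. The first is safety. The missing items include every laboratory limit on bleeding risk, in a trial where one arm receives a fibrinolytic. The exposure is not confined to that arm, because section 3.6 allows irrigation patients with poor drainage to be switched to fibrinolytic therapy. Appendix 1 foresees patients on anticoagulants, so the clotting limits can be expected to matter in practice.

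The second is whether the population can be verified. Section 3.2 defines the study population by poor drain output, and the primary outcome is drained volume. If the 150 ml rule is not checked and recorded, patients who already drain well could enter, and the trial record would not show it clearly.

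**Working it through.** No sample size, power or effect size enters this point, and the plan states no figure to reproduce. The check is an item-by-item comparison of section 3.4 with the sheet.

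| Section 3.4 exclusion | On the sheet's exclusion list? |
|---|---|
| 1. Refusal | No (arguably covered by the information-sheet line) |
| 2. Allergy to either drug | Yes |
| 3. Acute stroke | Yes |
| 4. Bleeding diathesis or active GI bleed | No (at most partly, through the major-haemorrhage item) |
| 5. Major surgery within 5 days | No |
| 6. Pneumonectomy on the infected side | No |
| 7. Bronchopleural fistula | No |
| 8. Pregnancy | No |
| 9. INR and APTT limits | No |
| 10. Platelet limit | No |

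**Exclusions carried over.** Two of ten, so 10 − 2 = 8 are missing. Treating refusal as handled by the consent step leaves 9 clinical items, of which 9 − 2 = 7 are missing. Crediting the major-haemorrhage item with item 4 as well leaves 7 − 1 = 6 of 9 missing. Most are missing on every count.

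**Laboratory limits.** Section 3.4 sets three (INR, APTT, platelets), and the sheet carries 0 of 3. The sheet's outcome table names only white cells and haemoglobin under the full blood count. It has no line for platelets, INR or APTT, so compliance with these limits cannot be verified from the sheet.

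**Exclusions only on the sheet.** One: the six-month haemorrhage or trauma item.

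**Inclusion.** The 150 ml/24 h rule and the pleural-fluid criteria are both absent from the sheet's list. The sheet does have a baseline cell for net volume drained, but it is not tied to the 150 ml limit or to the 24 hours after drain insertion.

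**Two test patients**, each otherwise eligible under both lists:

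- Platelets below 50000, no other exclusion: passes the sheet and fails section 3.4.
- Major trauma three months ago, no other exclusion: fails the sheet and can pass section 3.4.

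Each list admits someone whom the other bars, so neither is a summary of the other.

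**The case against.** A reader might infer that the sheet is the tool used at enrolment, so that barred patients will be randomised. The documents do not support that. The form is titled as a data collection sheet, and its fields run to discharge, readmission and 30-day mortality, so it is a case record form. Section 3.6 says that eligible patients will be offered participation, and eligibility is defined in section 3.4. No text tells staff to screen from the sheet. The printed condition for going on to data collection is that the information sheet was given, not that the listed criteria were met.

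The 150 ml rule is also stated in sections 3.2, 3.4 and 3.6, so leaving it off a record form does not remove it from the protocol. If both lists apply together, section 3.4 still bars every bleeding-risk patient it names, and the practical effect is one extra exclusion.

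A reader might also infer a third conflict, because section 3.6 defines a complex effusion on ultrasound as fibrin strands or septa "along with presence of loculations in pleural cavity", while section 3.4 asks only for strands or septations. That does not carry weight. Chapter 1 treats fibrinous septae and loculations as the same thing, and ultrasound is one of three features of which two suffice.

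These arguments limit the consequence to a possibility, but they do not remove the contradiction. Nothing says that section 3.4 overrides the sheet, and the sheet has no place to show that the laboratory limits were met. The section 3.7 flow chart is not shown in the text available, so whether it contained an eligibility step cannot be judged.

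**Conclusion.** The mismatch is established by reading the two lists side by side. Two of nine clinical exclusions are carried over and six or seven are missing. None of the three laboratory limits appears. The drainage rule and the pleural-fluid criteria are absent, and one exclusion exists only on the sheet.

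The consequence is conditional. If staff screen from the sheet, patients barred by section 3.4 could be enrolled, and patients whom section 3.4 accepts could be turned away. The documents do not show that this will happen, and they give no basis for estimating how many patients would be affected. What holds without that condition is that the governing list is unstated and that compliance with the INR, APTT and platelet limits cannot be verified from the sheet.

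The point concerns consistency between a form and the protocol. It implies no view on which criteria are clinically right.

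**What to change.** Reconcile the two lists into one, and print it identically in section 3.4 and on the Data Collection Sheet, with a tick box for each item. The sponsor should decide whether the six-month haemorrhage or trauma item belongs in both places or in neither.

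Add fields to the sheet for the INR, APTT, platelet count and 24-hour drain output, completed before randomisation, so that each limit can be checked against a recorded value.

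The cost is a form revision and a short protocol clarification. No extra tests should be needed, because section 3.4 cannot be applied without these values.
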